Exclusion Criteria	
 1. Active bacterial infection or fungal infection on the day of the ablation. 2. Patients with implantable pacemakers or other electronic implants. 3. Platelet count $<$ 50,000/mm³. 4. Patients with uncorrectable coagulopathy at the time of ablation. 5. Currently breastfeeding or pregnant (latter confirmed by serum or urine pregnancy test, per site's SOC). 6. Physical or psychological condition which would impair study participation. 7. ASA (American Society of Anesthesiologists) score of \geq 4. 8. Use of hydrodissection. 9. Systemic chemotherapy or radiation therapy for the liver, within 30 days prior to the study ablation procedure. 10. INR $>$ 1.8. 11. Patient has participated in an investigational clinical study within 30 days of the screening visit for this study. 12. Patient judged unsuitable for study participation by the performing physician for any other reason.
Safety Assessments	Patients will be evaluated for device-related or procedure-related AEs and all SAEs from the time of first probe puncture (Visit 2) through study completion (Visit 3).
Statistical Analysis	Categorical variables will be summarized descriptively by frequencies and associated percentages. Continuous variables will be summarized descriptively by number of patients, mean, standard

	
deviation, median, minimum, and maximum. Confidence intervals will also be provided for procedure-related variables.
 
The number and percentage of patients requiring probe repositions based on AC prior to the initial ablation will be summarized and a 95% confidence interval for the percentage will be provided. The number and percentage of patients in whom AC indicates repeat ablation is indicated based on insufficient margins following the initial ablation procedure will be summarized in a similar manner.
 
The number and percentage of patients experiencing device-related or procedure-related AEs and any SAEs will be summarized at the preferred term level.

Interim Analysis	There are no plans for interim analyses whose intent will be to stop the study early or to adapt the study design or planned number of patients.
Schedule of Activities	See Table 1 on the next page.

Table 1: Schedule of Activities

Visit No.	Visit 1:	Visit 2			Visit 3	Unscheduled Visit
Visit	Screening ¹⁹	Ablation Day			6 Weeks	Unsched. ¹⁸
Interval Windows	≤ 60 days of Visit 2	Day 0 = ablation of target lesion			(± 3 weeks) post-ablation	NA

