5.1 Primary Endpoints

The primary endpoints supporting the study objective are, as follows:

- Percentage of repositions informed by AC due to sub-optimal probe placement.
- Percentage of re-ablations informed by AC due to insufficient ablation margins.

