10.5 Primary Endpoint and Associated Hypotheses

The primary objective of this study will be assessed through recording whether feedback from the AC software indicates that the probe should be re-positioned prior to ablation as well as whether feedback from the AC software after the ablation procedure indicates that the margins are insufficient and hence a repeat ablation would be necessary. No hypotheses are specified for either of these endpoints as the study is descriptive in nature and will be used for estimation purposes.

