10.9 Analyses to be Conducted

Categorical variables will be summarized descriptively by frequencies and associated percentages. Continuous variables will be summarized descriptively by number of patients, mean, standard deviation, median, minimum, and maximum. Confidence intervals will also be provided for procedure-related variables.

Disposition of Study Patients

Patient disposition will be summarized using counts and percentages. The number and percentage of patients completed and discontinued along with the specific reasons for discontinuation will be tabulated by treatment group and in total.

Demographic and Baseline Characteristics

Summary statistics will be provided for patient demographics and pre-operative ablation characteristics.

Primary and Secondary Endpoint(s) Analyses

The number and percentage of patients requiring probe replacement/changes using the AC software prior to the initial ablation will be summarized and a 95% confidence interval for the percentage will be provided. The number and percentage of patients in whom the AC software indicates repeat ablation is indicated based on insufficient margins following the initial ablation procedure will be summarized in a similar manner.

The number and percentage of patients achieving technical success will be summarized and a 95% confidence interval will be provided. A similar summary will be provided for

technique efficacy.

The number and percentage of patients experiencing device-related and procedure-related AEs and all SAEs from the time of the first probe puncture (Visit 2) through study completion, or, if applicable, the day of early withdrawal, will be summarized by MedDRA preferred term and system organ class. Ninety-five percent confidence intervals may be provided for pre-specified adverse events of interest. The expected side effects related to MWA are as follows:

- Ascites (accumulation of fluid causing abdominal swelling)
- Biloma / bile leak (buildup of the bile within the abdomen / bile leak)
- Bile duct injury
- Bleeding requiring transfusion, embolization, or prolonged hospital stay
- Intrahepatic hematoma
- Pneumothorax or hemothorax
- Organ injury other than the liver (such as gastrointestinal injury/perforation or diaphragmatic injury/hernia)
- Fever
- General feeling of tiredness
- Infection
- Liver dysfunction
- Liver abscess
- Nausea
- Pain
- Pneumonia
- Pleural effusion

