b. At the lesion level: The number of lesions that had re-ablations informed by AC software due to insufficient ablation margins will be summarized by percentage and an exact 95% confidence interval of the percentage. Analysis will be conducted using FAS and PP analysis sets. The number of re-ablations informed by AC software is derived from the “Ablation Confirmation” form on the eCRF. A re-ablation informed by AC software is determined by an affirmative response to the question “Actions taken due to AC software indicating ablation margin was not complete” and followed by choosing at least one of the five action items that are listed on the form and these lesions represent the numerator for calculating the percentage. The denominator comprises with lesions for which the following option was chosen “No actions taken despite AC software indicating ablation margin was not complete” along with those presented on the numerator. Lesions belong to the group “No actions taken due to AC software indicating satisfactory margins” are not included to the numerator or denominator.

At the patient level: The numerator is “Number of patients for whom AC indicated that ablation margin was not complete for **at least one lesion** and surgeon took action.” The denominator is “Number of patients for whom AC indicated that ablation margin was not complete for **at least one lesion** and surgeon took action + Number of patients for whom no actions taken despite AC software indicating ablation margin was not complete for **at least one lesion**.” Patients who had all lesions belong to the group “No actions taken due to AC software indicating satisfactory margins” are not included to the numerator or denominator. An exact 95% confidence interval of the percentage will be estimated.

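### For the re-ablation primary endpoint the protocol counts patients in whom AC indicates insufficient margins, the SAP counts only cases acted on, and the protocol's percentage is never tabulated

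*SAP*

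**What the plan says.** **Protocol, margin endpoint.** Section 10.9 plans the number and percentage of "patients in whom the AC software indicates repeat ablation is indicated based on insufficient margins following the initial ablation procedure". The synopsis is almost identical: "patients in whom AC indicates repeat ablation is indicated based on insufficient margins following the initial ablation procedure". Section 10.5 says that the objective is assessed by recording whether "feedback from the AC software after the ablation procedure indicates that the margins are insufficient and hence a repeat ablation would be necessary". None of the three makes physician action a condition. The endpoint label in section 5.1 reads differently: "Percentage of re-ablations informed by AC due to insufficient ablation margins". The objective in section 5.0 asks whether AC feedback affects the physician's decisions.

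**Protocol, placement endpoint.** Section 10.5 records whether "feedback from the AC software indicates that the probe should be re-positioned prior to ablation". The synopsis refers to "patients requiring probe repositions based on AC prior to the initial ablation", and section 10.9 likewise speaks of patients who require probe changes.

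**SAP 9.4.1(b).** "A re-ablation informed by AC software is determined by an affirmative response to the question" about actions taken because AC showed an incomplete margin, "and followed by choosing at least one of the five action items that are listed on the form and these lesions represent the numerator". Lesions that AC flagged without any action are added to the denominator only. Lesions with satisfactory margins are in neither term. The patient-level fraction has the same structure, and part (a) for probe placement mirrors it.

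Protocol 7.1 allows the physician not to follow AC, asks for the reason, and says that this is not a deviation.

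**The concern.** A lesion in which AC shows an incomplete margin and the physician stops is an event under Protocol 10.9 and a non-event under SAP 9.4.1(b). Both documents foresee such cases: the protocol asks for a reason, and the SAP has a response category for them.

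The study tests no hypothesis, so these percentages and their intervals are the primary result. Two questions are in play. How often does AC find a problem? When it does, how often does the physician act? The protocol's statistical section asks the first for margins, while the SAP answers only the second. Protocol 10.1 says that the SAP supplements the protocol's analysis, but here it replaces a primary measure without saying so.

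**Working it through.** **Step 1. The plan's own figure.** Protocol 10.8 and SAP section 7 state that a 15% repositioning rate in 100 patients gives a 95% CI half-width below 7%.

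- Wald: 1.96 × √(0.15 × 0.85 / 100) = 0.06998, or 6.998%. The figure reproduces.
- Clopper-Pearson, the SAP's interval, for 15/100: 8.65% to 23.53%, half-width 7.44%.

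The figure reproduces with all 100 patients in the denominator. That supports reading the protocol's percentages as percentages of all patients ablated with AC, in line with the Full Analysis Set in 10.7. Section 10.9 does not spell the denominator out, so this remains an assumption.

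**Step 2. The margin definitions side by side.**

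| Outcome of AC margin check | Protocol 10.9 and synopsis | SAP 9.4.1(b) |
|---|---|---|
| Satisfactory | Non-event, in denominator | Excluded from both terms |
| Incomplete, physician acts | Event | Event |
| Incomplete, physician does not act | Event | Non-event, in denominator |

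The two numerators agree only if every indication is acted on. The denominators agree only if every check is flagged.

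**Step 3. Size.** The documents give neither the rate of AC indications nor the rate of acting on them, so all counts here are assumed. Let N be the patients checked, I those flagged, and A those acted on. With N = 100, I = 20, A = 14 and exact 95% intervals:

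- Indicated rate, I/N = 20/100 = 20% (12.7 to 29.2). This is the protocol's measure.
- Acted rate, A/N = 14/100 = 14% (7.9 to 22.4).
- Current SAP ratio, A/I = 14/20 = 70% (45.7 to 88.1).

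If 60%, 80%, 90% or 100% of the 20 indications are acted on, the SAP numerator is 12, 16, 18 or 20, against 20 under the protocol.

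**Step 4. What the SAP ratio cannot show.** Hold the acted share at 80% and vary I:

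| Flagged of 100 | Protocol measure | SAP ratio |
|---|---|---|
| 10 | 10% (4.9 to 17.6) | 8/10 = 80% (44.4 to 97.5) |
| 20 | 20% (12.7 to 29.2) | 16/20 = 80% (56.3 to 94.3) |
| 30 | 30% (21.2 to 40.0) | 24/30 = 80% (61.4 to 92.3) |

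The SAP ratio stays at 80% while the protocol's measure triples.

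**Step 5. Placement endpoint.** The contrast is clear only against section 10.5, which speaks of what AC indicates. The synopsis and 10.9 speak of patients requiring changes, which can be read as changes actually made.

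**The case against.** **The SAP follows other protocol text.** The objective concerns the physician's decisions, and section 5.1 speaks of re-ablations informed by AC. Advice that is not taken produces no re-ablation. This stands, and it means that the SAP does not simply contradict the protocol: sections 5.0 and 5.1 pull one way, and 10.5, 10.9 and the synopsis the other. It does not explain why the quantity that 10.9 says will be summarized has no table.

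**The SAP's rule is explicit.** It names the form response and both terms of the fraction. At lesion level the flagged count is the denominator and the acted count the numerator, and SAP 9.6 lists the no-action cases with reasons. This also stands. A reader can tell what the SAP computes. What is missing is a percentage over everyone AC checked, which would have to be rebuilt from a listing.

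**Timing.** SAP 9.4.1 omits the protocol's limits of before the initial ablation for placement and after it for margins. A reader might infer that probe changes made in later cycles inflate the repositioning rate, or that one failed margin is counted in both endpoints. The documents do not establish this. The form is not shown. Protocol 7.1 puts the AC placement check before ablation starts and handles post-ablation actions, including adding or removing probes, as a separate step. SAP 9.4.1 and 9.6 likewise keep placement and margin actions apart. The omission is a wording gap of unknown effect.

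**Conclusion.** The point holds for the re-ablation endpoint. The protocol's statistical section and synopsis define it by AC indication. The SAP defines it by indication plus action, over flagged cases only. The protocol's percentage is not tabulated and the change is not recorded. With the assumed counts, the same data read as 20%, 14% or 70% depending on the definition. These figures show scale and predict nothing; the gap between the two numerators closes only if physicians act on every indication.

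For the repositioning endpoint the indicated/acted contrast rests on section 10.5 alone. It would go too far to say that this contrast corrupts the repositioning rate meant to size a later study, because 10.9 and the synopsis can be read the SAP's way for that endpoint.

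The definition of a primary result is at stake, so it should be settled before the results are reported. Neither document needs to be declared right: both quantities are useful, provided that each is labelled.

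**What to change.** In SAP 9.4.1, report for each endpoint, at lesion and patient level and with exact 95% CIs:

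1. AC indicated a problem, over all lesions or patients in whom AC was used for that check.
2. AC indicated a problem and the physician acted, over the same denominator.
3. The present acted/indicated ratio, labelled as the share of AC indications acted on.

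The denominator in row 1 must change as stated. Over the SAP's current denominator that row would be 100% by construction (20/20 in the example). For margins, use the cases in which AC was used to assess margins, an item that SAP 9.6 already lists separately from its use for placement.

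Restate the protocol's timing: placement checks before the initial ablation, margin checks after it. Record in the SAP and the study report that the current definition departs from Protocol 10.9, and note that Protocol 5.1, 10.5 and 10.9 differ among themselves.

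The cost is SAP wording and two extra rows per endpoint. The responses are already on the Ablation Confirmation form, so no new data are needed for the rows. Applying the timing limits may need a check against the recorded ablation cycles.

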6.0 INVESTIGATIONAL PLAN

6.1 Overall Study Design and Plan - Description

This is a prospective, single-arm, multicenter study that will generate clinical data using the NEUWAVE Microwave Ablation System with Ablation Confirmation Software in patients undergoing MWA of at least one soft-tissue liver lesion. Note: A patient cannot have more than three lesions ablated during the procedure.

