9.4 Primary and Secondary Endpoints Analyses

9.4.1 Primary Endpoints Analyses

a. At the lesion level: The number of lesions that had repositioning of probe placement informed by AC software due to sub-optimal probe placement will be summarized by percentage and an exact 95% confidence interval of the percentage based on Clopper-Pearson method. Analysis will be conducted using FAS and PP analysis sets. The number of repositions informed by AC software is derived from the “Ablation Confirmation” form on the eCRF. A reposition informed by AC software is determined by an affirmative response to the question “Actions were taken due to AC software indicating probe placement was not satisfactory” and followed by choosing at least one of the three action items that are listed on the form and these lesions represent the numerator for calculating the percentage. The denominator comprises with lesions for which the following option was chosen “No actions taken despite AC software indicating probe placement was not satisfactory” along with lesions that are presented on the numerator. Lesions belong to the group “No actions taken due to AC software indicating satisfactory probe placement” are not included to the numerator or denominator.

At the patient level: The numerator is “Number of patients for whom AC suggested suboptimal probe placement for **at least one lesion** and surgeon took action.” The denominator is “Number of patients for whom AC suggested suboptimal probe placement for **at least one lesion** and surgeon took action + Number of patients for whom AC suggested suboptimal probe placement for **at least one lesion** and surgeon did not take action.” Patients who had all lesions belong to the group “No actions taken due to AC software indicating satisfactory probe placement” are not included to the numerator or denominator. An exact 95% confidence interval of the percentage will be estimated.

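### SAP 9.4.1 does not place a patient with one acted and one un-acted flagged lesion, so the patient-level denominators of both primary endpoints can count that patient twice

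*SAP*

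**What the plan says.** SAP 9.4.1 analyses each primary endpoint by lesion and by patient. The patient-level denominator is a sum of two terms.

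- **Endpoint (a), probe repositioning.** The numerator, which is also the first denominator term, is "Number of patients for whom AC suggested suboptimal probe placement for" at least one lesion, where the surgeon acted. The second term repeats this and ends "and surgeon did not take action".
- **Endpoint (b), re-ablation.** The numerator and first term are "Number of patients for whom AC indicated that ablation margin was not complete for" at least one lesion, where the surgeon acted. The second term is the number of patients "for whom no actions taken despite AC software indicating ablation margin was not complete for" at least one lesion.

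Only one group is removed from both numerator and denominator. That sentence begins "Patients who had all lesions belong to the group" and goes on to name the satisfactory category.

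The patient-level paragraphs ask for an exact 95% interval. The lesion-level paragraph of (a) names the method: "exact 95% confidence interval of the percentage based on Clopper-Pearson method". Protocol 6.1 sets the limit on lesions: "A patient cannot have more than three lesions ablated during the procedure".

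For technical success and technique efficacy, SAP 9.4.2 does give an explicit patient-level rule: every treated lesion must have succeeded. The primary endpoints have no corresponding rule for patients whose flagged lesions were handled differently.

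**The concern.** A patient with two or three lesions may have two of them flagged, one acted on and one not. The protocol allows this. Section 7.1 asks the physician to give a reason for not following an AC recommendation and states that not following it is not a deviation.

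The plus sign is safe only if the two terms cannot share a patient, and the SAP does not say that they cannot. The wording of (b) makes overlap easiest to reach, because its second term closely follows the lesion-level form option and then adds the at-least-one-lesion qualifier. A programmer rolling lesion records up to patients could set one indicator for any acted lesion and another for any un-acted flagged lesion, and add the two totals as the SAP directs.

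The study tests no hypothesis (Protocol 10.5, SAP 5), so these percentages and intervals are its primary result. Two programmers following the same text could report different values from the same data.

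**Working it through.** **The plan's own figure.** Protocol 10.8 and SAP 7 state a 95% half-width below 7% at a 15% rate with 100 patients. The Wald formula gives 1.96 × √(0.15 × 0.85 / 100) = 6.998%, so the figure reproduces. It has no bearing on the counting rule below.

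**Notation, for patients with at least one flagged lesion.**
- A = every flagged lesion acted on
- U = no flagged lesion acted on
- M = mixed, at least one acted on and at least one not

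**Three ways to form the ratio.**
1. Distinct patients: (A + M) / (A + U + M).
2. Disjoint reading, where the second term means no action on any flagged lesion: the terms are A + M and U, so the ratio is the same as in 1.
3. Overlapping reading, where the second term means at least one flagged lesion without action: the terms are A + M and U + M, so the ratio is (A + M) / (A + U + 2M).

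With c = A + U + M distinct flagged patients, reading 3 equals reading 1 multiplied by c / (c + M). It is never higher, it is equal when M = 0, and it is lower when M > 0 and anyone was acted on.

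**Size.** The documents give no number of flagged, multi-lesion or mixed patients, so all counts here are assumed. Intervals are Clopper-Pearson.

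| A, U, M | Distinct patients | Overlapping sum |
|---|---|---|
| 16, 2, 2 | 18/20 = 90.0% (68.3 to 98.8) | 18/22 = 81.8% (59.7 to 94.8) |
| 12, 3, 0 | 12/15 = 80.0% (51.9 to 95.7) | 12/15 = 80.0% (51.9 to 95.7) |
| 11, 3, 1 | 12/15 = 80.0% (51.9 to 95.7) | 12/16 = 75.0% (47.6 to 92.7) |
| 10, 3, 2 | 12/15 = 80.0% (51.9 to 95.7) | 12/17 = 70.6% (44.0 to 89.7) |
| 8, 3, 4 | 12/15 = 80.0% (51.9 to 95.7) | 12/19 = 63.2% (38.4 to 83.7) |

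The first row checks as 90.0% × 20/22 = 81.8%.

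**The interval.** Under reading 3 a mixed patient supplies one success and one failure, so the 22 units in the first row are not 22 patients and the binomial model behind the exact interval does not apply. The larger n does not make this interval look tighter: its width goes from 98.8 − 68.3 = 30.5 points to 94.8 − 59.7 = 35.1 points, because the percentage moves towards one half.

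**The case against.** The strongest reply is that the text can be read without any overlap. In (a), the at-least-one-lesion qualifier attaches to what AC suggested, while the action clause describes the surgeon and the patient. On that reading a mixed patient, whose surgeon did act, belongs only to the first group. In (b), the absence of action can also be taken to mean none at all for that patient. The exclusion sentence helps this reading: once patients with only satisfactory lesions are removed, those left among the assessed patients are exactly the patients with a flagged lesion. The reply adds that the study is descriptive, that the lesion-level percentages are unaffected, and that the listing in SAP 9.6 shows lesion number and action taken, so mixed patients would be visible.

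Most of this stands. The disjoint reading is natural in (a) and possible in (b), and it gives the right ratio. It also stands that the counts above are assumed. In the 20-patient row, 18 acted patients exceeds the 15 that a 15% rate in 100 patients would give for (a), and the study stopped below its planned size.

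What does not stand is the inference that the text is therefore sufficient. The exclusion sentence says who is left out, not how the rest are counted. A listing lets a reader discover the problem but does not settle the primary figure.

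**Conclusion.** The SAP leaves mixed patients undefined in both patient-level primary analyses, and its stated sum can count them twice, most clearly in (b). If it is applied that way and M > 0, the percentage is multiplied by c / (c + M) and the exact interval is built on an n that is not a count of patients. Each denominator holds only flagged patients, in a study that ended with fewer patients than planned, so one or two mixed patients could move the estimate by several points: from 80.0% to 75.0% or 70.6% with 15 flagged patients, under the assumed counts.

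A reader might infer that double counting is certain and that both reported percentages must be wrong. The documents do not support that, because a disjoint reading exists and no count of mixed patients is given; with none, the readings agree. Nor should an extreme case such as 20 of 20 becoming 20/40 = 50% be taken as a realistic bound. It would need every flagged patient to have at least two flagged lesions handled in opposite ways.

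This conclusion takes the flagged-only denominator as given, and assumes that the exact interval at patient level is Clopper-Pearson, as named at lesion level in (a).

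**What to change.** In SAP 9.4.1, in the patient-level paragraphs of both (a) and (b), replace the two-term sum with a single definition:

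- The denominator is the number of distinct patients with at least one lesion flagged by AC (probe placement not satisfactory in (a), margin not complete in (b)).
- A patient counts once in the numerator if action was taken on at least one flagged lesion.

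Reporting the number of mixed patients beside each percentage is optional, but would show whether the choice mattered.

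The cost is one sentence in each of two paragraphs, with no new data, because the eCRF already records the action taken for each lesion. If the SAP is not amended, SAP 9.1 already requires departures from it to be identified in the statistical output and documented in the clinical study report, and the counting rule used could be stated there.
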